1.7 Drugs/Devices/Biologics

A. Schedule and Administration

N/A

B. Drug/Device Accountability and Storage Methods

N/A

1.8 Specimen Collection

A. Primary Specimen Collection

N/A

B. Secondary Specimen Collection

N/A

1.9 Data Collection

A. Primary Data Collection

- **Location:** Data will be collected online using the secure Qualtrics survey platform
- **Process of Data Collection:** Participants will log into Qualtrics from their own device and complete survey data remotely. We will review collected data on a weekly basis for completion.
- **Timing and Frequency:** Data collection will take place during a single session during the 2022-2023 and 2023-2024 school year.
- **Procedures for Audio/Visual Recording:** N/A
- **Study Instruments:** The survey instruments have been used in previous research studies. All measures are listed in section 1.6 and copies of all measures have been uploaded to the eIRB application (Appendix B).
- **Ethnographic Studies, Interviews, Or Observation:** N/A
- **Subject Identifiers:** No identifying information will be collected from the participants. Students log into the SONA system which manages participation credit without the research team having to collect any identifiable information from participants.

B. Secondary Data Collection

N/A

1.10 Timetable/Schedule of Events

This is a single visit study; thus all study procedures will happen after consent in one session.

2.2 Research Staff Training

All persons assisting with the research will maintain active CITI Training Certifications.

2.3 Other Resources

The study will draw on the students in the Psychology Subject Pool which is maintained by the Department of Psychology. Because the study is conducted online, there are no additional physical resources needed. There are no additional medical or psychological resources needed because the study poses no reasonably foreseeable risks to subjects.

2.4 Research Sites

Data will be collected and stored online in the secure Qualtrics Server hosted by Rutgers University.

3.0 Multi-Center Research

N/A

4.0 Subject Considerations

4.1 Subject Selection and Enrollment Considerations

A. Method to Identify Potential Subjects

Potential subjects for the study will be identified by their current enrollment in Introduction to Psychology (50:830:101) or Method and Theory of Psychological Research (50:830:255).

B. Recruitment Details

The study will be posted to the Psychology Subject Pool which is hosted on the website SONA, maintained by the Psychology Department. Students are given the opportunity to participate in research as part of their class experience and receive class credit for participation. No additional recruitment will take place.

C. Subject Screening

Describe whether and how individuals will be screened for eligibility and by whom.

▪ **Inclusion Criteria**

Students enrolled Introduction to Psych (101) and Method and Theory (255) who are between the ages of 18-35 will be eligible to participate. Students will be asked to confirm that they are in the specified age range in Qualtrics before completing the informed consent form.

▪ **Exclusion Criteria**

Students under 18 years of age or over 36 or older will be excluded.

D. Privacy Protections

This study will not collect any identifiable participant data. Sona creates a unique randomly generated participant ID that is used in Qualtrics to collect data. The Sona system will separately maintain participant email addresses for the purpose of assigning class credit, but this will not be linked to the data collected in Qualtrics. When a student completes the survey in Qualtrics, they are returned to the Sona system so that they may receive class credit. Researchers will only identify data by the unique randomly generated participant ID.

4.2 Obtaining Identifiable Information About Non-Subjects

N/A

4.3 Number of Subjects

A. Total Number of Subjects

It is expected that 500 students will be screened to accrue 400 complete subjects needed to analyze the hypotheses of this study.

B. Total Number of Subjects If Multicenter Study

N/A

C. Feasibility

The Psychology Subject Pool typically has between 500-700 students in the fall and 200-300 students in the spring, making recruiting feasible in one-two school years.

4.4 Consent Procedures

A. Consent Process

- Location of Consent Process**

The consent process will take place in Qualtrics after participants confirm eligibility. Participants will be required to agree to the document by checking a box in order to access the survey tools.

- Ongoing Consent**

N/A

- Individual Roles for Researchers Involved in Consent**

Researchers will develop the informed consent document but will not otherwise be directly involved in obtaining consent from participants.

- Consent Discussion Duration**

Participants will be given the consent form at the beginning of the study and will be allowed to consider participation for as long as possible. Contact information will be available for the principal investigator should the participant have questions or concerns regarding the study or its procedures.

- Coercion or Undue Influence**

The consent document will clearly state that participation in the study is voluntary. Additionally, course instructors will make clear to students that participation is voluntary and students will be given an alternative assignment for course credit should they not want to participate in research.

- Subject Understanding**

Before a subject can access the study survey tools, they will be required to indicate that they understand the nature of the study and consent to participate.

- Protecting Privacy**

Surveys will be completed online on the students' electronic devices, no one will know of their participation.

B. Waiver or Alteration of Consent Process

- Waiver or Alteration Details**

- N/A
- **Destruction of Identifiers**
 N/A
- **Use of Deception/Concealment**
 Participants will be given general details about the study activities and potential risks; however they will not be provided with specific hypotheses of the study. Specifically, the participants will be told that the study is interested in learning about students' knowledge and attitudes about participating in the NMDP, but students will only view one of the potential conditions (rational or emotional) to understand if these different methods differentially impact intentions to participate in the registry. Omitting information about the specific hypotheses is necessary to fairly test hypotheses and avoid demand characteristics.
 - a. **Minimal Risk Justification**
 This study is minimal risk because we will be providing students with very brief information about the reasons individuals may decide to participate in the NMDP. This information is like that provided to encourage participation in other donation programs such as blood donation that is regularly broadcasted on radio and television advertisements.
 - b. **Alternatives**
 Any alternative that involves divulging true purpose would not allow a fair test of the hypotheses.
 - c. **Subject Debriefing**
 All participants will be provided with links to learn more about the Be the Match program at the end of the study. Participants will also be given the opportunity to ask questions of the research team through the PI's email address.

C. Documentation of Consent

- **Documenting Consent**
 Subjects' consent to participate in the study will be documented in their survey results, as they will be required to indicate that they understand the study and consent to participate before they are able to access the survey tools.
- **Waiver of Documentation of Consent (i.e., will not obtain subject's signature)**
 Subject's will indicate "I agree" or "I do not agree" in the online consent form, therefore a waiver of the documentation of consent is requested.

4.5 Special Consent Populations

A. Enrolling Minors-Subjects Who Are Not Yet Adults

- **Parental Permission**
 We will only enroll students who are 18 or older
- **Non-Parental Permission**
 N/A
- **Assent Process**
 N/A
- **Documentation of Assent**
 N/A
- **Reaching Age of Majority During Study**
 N/A

B. Enrolling Wards of the State

- N/A
- **Research Outside of NJ Involving Minors**
 N/A

C. Enrolling Non-English-Speaking Subjects
N/A

- **Process for Non-English-Speaking Subjects**
N/A
- **Short Form Consent for Non-English Speakers**
N/A

D. Enrolling Adults Lacking Decision-Making Capacity (Surrogate Consent)
N/A

- **Assessing Adult Capacity to Consent**
N/A
- **Selecting a Surrogate & Consent Process**
N/A
- **Subject Assent**
N/A
- **Selecting a Witness to the Surrogate Consent Process**
N/A
- **Removing a Subject**
N/A

E. Special Consent Considerations

The following steps will be taken to ensure that students do not feel coerced by faculty to participate in the research:

- a. Students will be offered alternate assignments to participation in research, thus not participating will not affect their course grade.
- b. Students will be able to select participation based on the study title and brief study description. Thus, they can elect not to participate in this specific study.
- c. Language has been added to the consent form explaining that participation is voluntary and that deciding to take part in the study or withdrawing will not impact their standing in their psychology courses.

4.6 Economic Burden and/or Compensation for Subjects

A. Expenses

Participants will not incur any direct or indirect costs because of their participation in the study.

B. Compensation/Incentives

Participants will not receive any direct or indirect compensation or incentives for participation in this study.

C Compensation Documentation

N/A

4.7 Risks of Harm/Potential for Benefits to Subjects

A. Description of Risks of Harm to Subjects

- **Reasonably Foreseeable Risks of Harm**

The foreseeable risks associated with participating in this study are due to the study content being related to cancer and other blood-based conditions. Participants may find it distressing to read about a child with cancer in need of a bone marrow transplant.

- **Risk of Harm from an Intervention on a Subject with an Existing Condition**

There are no documented risks to participation in this type of study.

- **Other Foreseeable Risks of Harm**

Participation will be kept confidential and anonymous. Researchers will not have access to study names or identifying information.

- **Observation and Sensitive Information**

N/A

B. Procedures which Risk Harm to Embryo, Fetus, and/or Pregnant Subjects

N/A

C. Risks of Harm to Non-Subjects

N/A

D. Assessment of Social Behavior Considerations

N/A

E. Minimizing Risks of Harm

Participants will be told the purpose of the study before consent, including that we are trying to learn about what motivates individuals to donate bone marrow/stem cells for patients with cancer and blood-based health conditions. Should they be uncomfortable with this study content they can elect not to participate. Further, should participants become uncomfortable while answering any questions or while reading about the reasons patients need a transplant, they can skip questions or stop participation at any time. Finally, participants will be provided with the principal investigator's contact information should they need to discuss the study content further.

- **Certificate of Confidentiality**

N/A

- **Provisions to Protect the Privacy Interests of Subjects**

N/A

F. Potential Direct Benefits to Subjects

There are no direct benefits for participating in the study, although their participation may help increase diverse enrollment in the NMDP in the future.

5.0 Special Considerations

5.1 Health Insurance Portability and Accountability Act (HIPAA)

N/A

5.2 Family Educational Rights and Privacy Act (FERPA)

N/A

5.3 Code of Federal Regulations Title 45 Part 46 (Vulnerable Populations)

Rutgers-Camden undergraduate students will be enrolled and the study and a considered a vulnerable population because of the potential for students to feel coerced by faculty and instructional staff.

A. Special Populations

Following the procedures for using students as subjects in the Rutgers Research HSPP the following steps will be taken to reduce the possibility for students to feel coerced into participation.

- 1) The Principal Investigator teaches one section of Method and Theory but will not recruit in class. Students will be given the opportunity to select which studies they would like to

participate in and will not be penalized in any way for participating or not participating in this specific study.

- 2) Students in the Psychology Subject Pool will be given an alternate assignment should they elect to not participate in research.
- 3) Students' grades will not be impacted if they do not consent to participation or if they choose to withdraw from the study. This will be explained to students as part of the consent process.

5.4 General Data Protection Regulation (GDPR)

N/A

5.5 NJ Access to Medical Research Act (Surrogate Consent)

N/A

6.0 Data Management Plan

6.1 Data Analysis

Data will be analyzed using ANOVAs and multivariate linear regression models.

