1.5 Sample Size Justification

Prior research has demonstrated an effect size of $w=0.38$ (medium effect) between an emotional and rational appeal, thus we expect a medium effect size (Studts et al., 2010). In order to compare the effect of the two conditions (emotional/rational) by race/ethnicity (White, African-American, Latinx considered as the primary groups represented, recognizing there will be others) we will need 300 participants to have 85% power to detect a medium effect with a p-value of 0.05. To be conservative and ensure we have a large enough sample of each race/ethnicity group, we will seek to enroll 400 students.

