History of transplant/donation	Previous research by Narayanan et al., (2016) has included these 15 items to assess an individual's familiarity with the transplant and donation process.
Motivations to donate	Participants are asked to rank order 11 possible reasons that they may decide to register for the transplant registry (Bart et al., 2014). Participants will complete this measure before and after the Emotional/Rational condition presentation.
Attitudes towards bone marrow transplant	Participants will be asked 9 questions about their attitudes towards joining the bone marrow registry and donating stem cells at a later date. This measure has been used in previous research (Narayanan et al., 2016).
Ambivalence	The Simons Ambivalence Scale is a 7-item scale developed to assess feelings about solid organ donation(Gardner, 1987). The measure has been modified for stem cell donor participation (Fingerut et al., 2020) and 4 of the 7 items will be used in the current study.

B. Dependent Variables or Outcome Measures

The primary dependent variable is intentions to register in the bone marrow transplant registry.

Secondary Dependent Variables: Participants will be asked about how factual and how emotional they perceived the appeal they received is to determine if the manipulation worked. We will also ask about their current mood again.

Construct/Measure	Description
Intentions to register	Participants will be asked 2 questions about whether they will register and the rate the likelihood of registering. They will be asked these questions before and after the experimental manipulation.
Manipulation Check	Participants will be asked to rate how emotional and how factual the appeal they received was on a 1-7 scale.
Mood	Participant mood will be assessed pre/post survey, asking participants to rate their current mood on a 1-10 scale.

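### Section 6.1 does not say whether the pre-appeal intention answers are used or which contrast tests hypothesis 5, and the 85% power in section 1.5 does not describe a difference in appeal effect between students of color and white students

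*Combined protocol and SAP*

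**What the plan says.** Section 1.6 B states: "The primary dependent variable is intentions to register in the bone marrow transplant registry". The measure consists of two items: "Participants will be asked 2 questions about whether they will register and the rate the likelihood of registering". On timing it adds: "They will be asked these questions before and after the experimental manipulation". Neither item is ranked above the other, and no scoring rule is given.

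Section 6.1 contains only this: "Data will be analyzed using ANOVAs and multivariate linear regression models". It names no outcome item, no pre-appeal term, no interaction and no primary contrast.

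Section 1.5 gives the purpose of the sample size as to "compare the effect of the two conditions (emotional/rational) by race/ethnicity", listing White, African-American and Latinx as the main groups. It cites an "effect size of $w=0.38$ (medium effect) between an emotional and rational appeal" from earlier research and concludes that "we will need 300 participants to have 85% power to detect a medium effect with a p-value of 0.05". It then adds a margin: "we will seek to enroll 400 students". Section 4.3 A confirms 400 complete participants.

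Objective 3 (section 1.1 A) compares the strategies by race and ethnicity. Hypothesis 5 (section 1.1 B) uses two groups rather than three: it expects the rational appeal to do better among students of color than among white students. Section 1.3 A randomizes the appeal, by sex.

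**The concern.** Section 1.5 justifies the sample size by the race/ethnicity comparison, so a reader will take the 85% as the power of that comparison. Two different questions fit its wording:

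- Does the appeal work within a given race/ethnicity group?
- Does the appeal effect differ between groups?

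The second is what hypothesis 5 needs if it is to be a randomized comparison, and at the same N it is the harder one to answer.

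The plan also collects the variable that would help most, the same rating taken minutes earlier, without saying that the analysis will use it. Post-appeal only, change score and baseline-adjusted models all remain open, for either of two questions, and the choice could be made after the data are seen. At stake are the interpretability of objective 3 and hypothesis 5 and a gain in precision that costs nothing.

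**Working it through.** **Inputs from the protocol.** N = 300, power 85%, alpha 0.05, w = 0.38 described as medium, three named groups (section 1.5); 400 complete participants (sections 1.5 and 4.3 A); two groups in hypothesis 5 (section 1.1 B).

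**Assumptions, because the protocol gives no figure.** Medium means w = 0.30 for a yes/no answer or d = 0.5 SD for the rating. Allocation is 1:1. Every participant is classed as white or of color, with a white share of 33–60%. The pre/post correlation r of the rating is 0.5–0.7. Tests are two-sided.

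**Step 1: reproduce the 300.** For a chi-square test, noncentrality is λ = n·w².

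- w = 0.30, n = 100, 1 df: λ = 9.0, power 85.1%. Three groups of 100 give 300.
- w = 0.38, n = 100, 1 df: λ = 14.4, power 96.7%. Here 63 participants suffice for 85%, and 3 × 63 = 189. So the cited w = 0.38 does not itself lead to 300 with a 1-df test.

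For a two-arm comparison of the rating, λ = n·d²/4.

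- d = 0.5, n = 150, df 1 and 148: λ = 9.375, power 86.0%. Two groups of 150 give 300. The exact need is 146 per group, and 2 × 146 = 292.
- d = 0.5, n = 100, df 1 and 98: λ = 6.25, power 69.7%.

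The figure of 300 is therefore reproducible for either question, as emotional versus rational **within** a race/ethnicity group. The protocol does not say which question, test or grouping was used.

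**Step 2: overall appeal effect, rating, d = 0.5.** λ = N·d²/4.

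- N = 300: λ = 18.75, power 99.1%.
- N = 400: λ = 25, power 99.9%.

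**Step 3: hypothesis 5 as a difference in appeal effects, N = 400.** With two equal arms, the appeal effect in a group of size n has variance 4/n (SD units). The difference D between white students (nW) and students of color (nC) then has SE² = 4/nW + 4/nC, and λ = D²/SE². Take D = 0.5, for example an appeal effect of 0.5 SD in one group and none in the other. Adjustment for the pre-appeal rating multiplies SE² by (1 − r²): 0.75 at r = 0.5 and 0.51 at r = 0.7.

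| White share | SE² | λ, unadjusted | Power, unadjusted | Power, r = 0.5 | Power, r = 0.7 |
|---|---|---|---|---|---|
| 1/3 | 0.0450 | 5.56 | 65.2% | 77.5% | 90.9% |
| 40% | 0.0417 | 6.00 | 68.6% | 80.6% | 92.8% |
| 50% | 0.0400 | 6.25 | 70.3% | 82.1% | 93.7% |
| 60% | 0.0417 | 6.00 | 68.6% | 80.6% | 92.8% |

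The first row in full: nW = 133.3 and nC = 266.7, so SE² = 0.030 + 0.015 = 0.045 and λ = 0.25/0.045 = 5.56. At r = 0.5, λ = 5.56/0.75 = 7.41; at r = 0.7, λ = 5.56/0.51 = 10.9. Degrees of freedom are 1 and 396 unadjusted, 1 and 395 adjusted.

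**The case against.** **The plan does not exclude the pre-appeal answer.** This stands. A reader might infer that the stated analysis ignores it, but section 6.1 is silent, and both ANOVA and linear regression can take it as a term. The criticism is that the choice is left open.

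**The sample size is not wrong.** This also stands. A reader might infer that 300 is a miscalculation, or that the 85% cannot apply to the rating. Step 1 contradicts both: 300 follows from a chi-square reading in three groups, and 86.0% is reached on the rating in two groups. Section 1.5 also gives an effect size, a label for it and the groups, so the figure is partly anchored.

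**The main comparison is safe.** Section 1.6 A makes the appeal the primary independent variable, and its overall effect has over 99% power at 0.5 SD. Hypothesis 5 is one of six. The documents therefore do not support calling the trial underpowered as a whole.

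**A 0.5 SD difference between effects is not the same quantity as a 0.5 SD effect.** Correct. The two powers should not be presented as one effect under two tests. The 0.5 SD difference is an assumption about the interaction, and a larger true difference would have more power.

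**Hypothesis 5 can be read as white students versus students of color inside the rational arm.** Its wording allows that. With 150 in that arm (N = 300), d = 0.5 and a normal approximation, power is 82.3%, 85.1% and 86.5% at white shares of 1/3, 40% and 50%, close to the stated figure. But that comparison is not randomized, and pre-existing differences in intention between the groups would enter it. Nor does it match section 1.5, which speaks of comparing the two conditions.

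**Conclusion.** The point holds in a limited form. The plan leaves open the primary question, the use of the pre-appeal answer and the contrast for hypothesis 5. The 85% at 300 fits an appeal comparison within a race/ethnicity group. It does not state the power for a difference in appeal effect between students of color and white students.

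At the planned 400, that contrast has 65–70% power unadjusted and 78–94% adjusted. These figures rest on an assumed 0.5 SD difference in appeal effects, 1:1 allocation, a white share of 33–60% and a pre/post correlation of 0.5–0.7, none of which the protocol gives. What does not depend on the exact values is the direction: the interaction is estimated less precisely than the overall appeal effect, and a pre-appeal rating correlated with the post-appeal rating improves that precision. The change should be made before analysis, but nothing here prevents the trial from running.

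**What to change.** 1. **Sections 1.6 B and 6.1.** Name the likelihood rating as the primary question. Analyze the post-appeal rating by linear regression on appeal, adjusted for the pre-appeal rating. Test hypothesis 5 as the interaction of appeal with students of color versus white students, because a comparison of race/ethnicity groups inside the rational arm is not randomized.
2. **Section 1.5.** Say that 85% at 300 refers to the appeal effect within a race/ethnicity group, and give the question, the test and the numeric effect used. State the lower power for the hypothesis 5 interaction at 400, with the assumed pre/post correlation, and report that contrast as an estimate with a confidence interval. Under the assumptions above, the 95% half-width (1.96 × SE) would be about 0.39–0.42 SD unadjusted (SE 0.200–0.212) and 0.28–0.36 SD adjusted (SE 0.143–0.184).

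The cost is wording in three sections. No new data or participants are needed, because the pre-appeal rating is already collected.
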